11.2. Reporting of Adverse Events

The Investigator is required to report all reportable SAEs and UADE's within 24 hours after first learning of the event to the Sponsor (**Table 11-1**). In addition, where local country regulatory authorities specially require a more stringent definition or additional requirement, the local regulation should also be complied with.

The primary method of reporting SAEs to the sponsor will be through the electronic study database on the Adverse Event eCRF.

The primary method of reporting UADE's is through SAE hotline email.

If the database is unavailable or not accessible the Investigator may send the information to the SAE email hotline.

The Investigator shall provide all requested supporting documentation for reported SAEs or AEs (blinded/de-identified as to subjects' identity) through the SAE Hotline or to the monitor and/or clinical team via email as requested. The Investigator shall complete data entry in the study Electronic Data

ADVANCE Clinical Investigation Plan			
PR-NV16099	Version C	Page 103 of 144	Medtronic

Capture (EDC) database with the same information provided on the paper form as soon as the database becomes available.

Table 11-1. Expedited Adverse Event and Device Specific Event Reporting Requirements

SAEs / DD with SADE	$\label{eq:starses} Investigator will notify {\tt Sponsor} of all {\tt SAEs} and {\tt Device} {\tt Deficiencies} with {\tt SADE}$	
potential	potential within 24 hours of being aware of the event.	
Primary method of	Corresponding eCRF (e.g., Adverse Event CRF or Device Deficiency CRF) in	
reporting	study EDC database	
Sponsor 24 Hour	Email:	
SAE/UADE Hotline	To be used as back-up in event that database if unavailable or inaccessible	
contact information:	within required reporting timeline or for reporting all UADE's.	

As additional information becomes available, copies of source documentation which contain significant information related to the event such as operative reports, imaging studies, discharge notes and subject summaries etc. may be requested for a complete evaluation of the event by the sponsor or CEC.

In regard to subject deaths, a de-identified copy of the death certificate and a de-identified copy of the autopsy report, if applicable, is to be sent to the Sponsor. Any other source documents related to the death should also be provided to the Sponsor and should be blinded/de-identified as to the subject's identity. In the event that no source documents are available, the Investigator is requested to describe the circumstances of the subject's death in a letter, e-mail or other written communication to the Sponsor.

The Investigators are required to comply with their local Safety reporting requirements per their region/IRB/REB.

UADEs/USADEs have expedited reporting requirements. UADEs must be reported by the Investigator to the Sponsor via email provided above within 24 hours and the reviewing IRB/REB per IRB/REB reporting requirement, but in no event later than 10 working days after the investigational site first learns of the event (CFR 812.150(a)(1)).

11.3. Device Deficiency

Device Deficiency is defined as inadequacy of a medical device with respect to its identity, quality, durability, reliability, safety or performance (ISO 14155:2011 3.15).

Note that device deficiencies include malfunctions, use errors, and inadequate labeling.

ADVANCE Clinical Investigation Plan Image: Clinical Investigation Plan Image: Clinical Investigation Plan PR-NV16099 Version C Page 104 of 144 Medtronic

All device deficiencies should be reported to the Sponsor on the DD eCRFs in a timely manner.

Device Deficiencies that have the potential to cause a serious adverse device effect shall be reported to the sponsor within 24 hrs of site's awareness of the event.

These should be reported to the local competent authorities and IRBs/REBs as required per local requirements.

When a DD is observed, every effort should be made to return the device and its packaging to the Sponsor in a timely manner.

All Qualified Investigators must report product complaints to the sponsor (i.e., any Medtronic personnel) and Health Canada as required by governing law (i.e., Canada Medical Device Regulations 1998 (SOR/98-282).

PR-NV16099

Version C

Page 105 of 144

12. Data Review Committees

To avoid and minimize bias, an independent CEC, Imaging Core Laboratory, and DMC will be in place to assess adverse events, occlusion and parent artery stenosis, and oversee the safety of the trial respectively.

12.1. Clinical Events Committee

A CEC shall be comprised of a minimum of three (3) physicians knowledgeable in the appropriate disciplines and medical specialties pertinent to the disease state being evaluated in this clinical study and will be responsible for an independent, objective and consistent review of AEs.

Event level adjudications will be performed by a single CEC member for start and stop dates, seriousness, causality assessment, severity and outcomes for all adjudicable adverse events per CEC charter.

The CEC will independently adjudicate each subject to pre-specified Events Of Interest (EOI) which indude the primary endpoint, secondary safety endpoints, and pre-specified events of interest per **Section 10.1**.

The CEC can request additional source documentation and any potential imaging obtained in support of the adverse event to assist with adjudication.

12.2. Imaging Core Laboratory

To objectively and consistently assess imaging data, an imaging protocol will be provided to the site. The imaging core laboratory will be responsible for the qualitative image analysis to determine aneurysm occlusion, parent artery stenosis, and discernible device movement.

12.2.1. Screening Eligibility Review

The core lab will be responsible for review of screening images to determine suitability for treatment in the study. In this role, the core lab will perform measurements to confirm the anatomical dimensions included in the eligibility criteria.

The reviewing committee (Physician Screening Committee) will be responsible for determining subject eligibility in the study. Further details on the Physician Screening Committee will be provided in the core lab charter.

12.2.2. Pre-Procedure Anatomy

Baseline imaging will be reviewed to assess baseline aneurysm and parent artery characteristics.

ADVANCE Clinical Investigation Plan Advance Advance PR-NV16099 Version C Page 106 of 144 Medtronic

12.2.3. Aneurysm Occlusion

Post-procedure and follow-up angiograms will be reviewed to assess an urysm occlusion according to the Raymond Roy Scale¹ (**Figure 12-1**).

[figure not shown]

Figure 12-1. Raymond Roy Scale for Grading Aneurysm Occlusion

- **Class 1: Complete Occlusion** = Complete obliteration of the aneurysm
- **Class 2: Residual Neck** = Persistence of any portion of the original defect of the arterial wall as seen on any singe projection, but without opacification of the aneurysmal sac
- Class 3: Residual Aneurysm = Any opacification of the aneurysmal sac

12.2.4. Parent Artery Stenosis

Post-procedure angiograms will be reviewed to assess stenosis in the parent artery across the entire Pipeline[™] Vantage Device implant. Vessel stenosis will be measured and judged according to the scale in **Table 12-1** in cases, where paired imaging is available for DSA. If DSA is unavailable, flow limiting stenosis (> 50%) vs. non-flow limiting stenosis (≤ 50%) will be assessed by CTA images.

Category	Degree of Stenosis
0	1–25%
1	>25 –≤50%
2	>50 – ≤75%
3	>75–100%

Table 12-1	. Stenosis Grading Scale
------------	--------------------------

12.3. Data Monitoring Committee

The DMC will be an independent group that will serve as a data monitoring committee. The DMC will be comprised of representatives from multiple disciplines including but not limited to neurology,

ADVANCE Clinical Investigation Plan Image: Clinical Investigation Plan Image: Clinical Investigation Plan PR-NV16099 Version C Page 107 of 144 Medtronic

biostatistics/epidemiology, neurosurgery and interventional neuroradiology that are independent of the clinical sites.

In the safety monitoring role, this board shall provide recommendations to the Sponsor regarding in the conduct of the clinical study. The DMC will establish proposed safety monitoring criteria for the study and will establish and document any required analysis time points for assessing safety. The group will also establish a DMC Charter which will describe the DMC operating procedures.

PR-NV16099

13. Statistical Design and Methods

13.1. General Principles

A detailed statistical analysis plan (SAP) will be finalized prior to performing any analyses to expand upon the statistical methods presented below. Summary tables will summarize data for all subjects combined. All recorded data will be presented in the individual data listings sorted by site patient, and date of observation.

13.2. Sample Size Determination

The target sample size for this clinical investigation is 100 patients enrolled and treated and followed for safety events with the expectation of having digital imagery at 1-year post-procedure on a minimum of 80 patients.

Sample size estimation for the primary safety endpoint was initially based on recommendations by the FDA considering the precision of the estimates. For the primary safety endpoint, the incidence of major stroke in the territory supplied by the treated artery or neurological death at 1 year, with an incidence as high as 8%, a sample size of 100 subjects will provide a precision of approximately ± 5.5%, which is considered to be reasonable.

The basis for establishing the a priori threshold for the primary safety endpoint at 14% is rooted in the derivations presented in the table presented below, predicated on a population for analysis of 100 patients (with up to 140 subjects enrolled). Simulations were prepared in SAS assuming an observed incidence in the ADVANCE IDE study of primary safety events ranging from 5.6% to 6.9%. Scenarios 1 through 9 reveal a power greater than 80% (**Table 13-1**).

Simulation Scenario	a priori Threshold (proportion)	Observed Incidence (proportion)	Actual Type 1 Error Rate	Power (percent)
1	0.14	0.0560	0.0492	89.19
2	0.14	0.0570	0.0492	88.29
3	0.14	0.0580	0.0492	87.36
4	0.14	0.0590	0.0492	86.38
5	0.14	0.0600	0.0492	85.37
6	0.14	0.0610	0.0492	84.32
7	0.14	0.0620	0.0492	83.23
8	0.14	0.0630	0.0492	82.11
9	0.14	0.0640	0.0492	80.96

Table 13-1. Estimated Power Over a Range of Possible Primary Safety Outcomes with 100 Patients (a priori threshold of 14%)

Medtronic Controlled Information

This document is electronically controlled

056-F275, v A Clinical Investigation Plan Template

ADVANCE Clinical Investigation Plan					
PR-NV16099)	Version C	Page 109 of 144		Medtronic
10	0.14	0.0650	0.0492	79).77
11	0.14	0.0660	0.0492	78	3.55
12	0.14	0.0670	0.0492	77.30	
13	0.14	0.0680	0.0492	76.02	
14	0.14	0.0690	0.0492	74	l.72

Although the power is less than 80 when the incidence of safety events is 6.5% or higher, the power is still adequate when contrasted against the actual upper bound of the 1-sided 97.5% exact binomial confidence interval. Specifically, if 7 of the 100 patients experience a primary safety event, the upper bound of the 1-sided 97.5% exact binomial confidence interval would be 13.89% and below the 14% threshold.

For the primary effectiveness endpoint, the power was estimated for an observed rate between 65% to 80% considering sample sizes from 80 to 100 patients. With a type 1 error rate of 2.5%, 100 patients would have 82.8% power to reject the null hypothesis if the observed incidence of complete aneurysm occlusion without parent artery stenosis was 65%. Under the same scenario with 80 patients, the power would be 83.5% if the observed incidence of complete aneurysm occlusion without parent artery stenosis or retreatment would need to be a minimum of 71% and 69%, respectively. Requiring a minimum sample size of 100 patients with 95% power translates into a minimum incidence of complete aneurysm occlusion without parent artery stenosis or retreatment artery stenosis of 69% which is in-line with the previous results with the results from previous Pipeline studies.

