stenosis (≤ 50%) or retreatment of the target aneurysm at 1-year post- procedure. The incidence will be summarized using counts and percentages; the 1-sided upper bound of the 97.5% confidence limit for the incidence will be evaluated relative to the a priori threshold of 50%. The hypothesis for evaluating the primary effectiveness endpoint is stated below: H _o : Incidence at 1-year post-procedure of complete aneurysm occlusion without retreatment or significant parent artery stenosis is ≤ 50.0% H _a : Incidence at 1-year post-procedure of complete aneurysm occlusion without retreatment or significant parent artery stenosis is > 50.0% The pre-specified threshold of 50% for effectiveness endpoint is based on the effectiveness threshold of the recent PREMIER study with the Pipeline™ Device. This threshold must be exceeded at a certain magnitude to reject the null hypothesis and merely serves a statistical boundary for analysis. If the upper bound of the 1-sided 97.5% exact binomial confidence interval is >50%, the primary effectiveness endpoint will have been met.
primary effectiveness endpoint wirnave been met.
Sample Size The target sample size for this clinical investigation is 100 patients enrolled and
treated and followed for safety events with the expectation of having digital imagery at 1-year post-procedure on a minimum of 80 patients. To calculate
the sample size, simulations were prepared in SAS assuming an observed incidence in the ADVANCE IDE study of primary safety events ranging from 5.6%
to 6.9%. With 100 patients and an observed incidence of safety event from 5.6% to 6.4%, the power exceeded 80%. Between the ranges of 6.5% to 6.9%, the power ranged from 79.8% to 74.7% for the primary safety endpoint and
slightly below 80%. Although the power is less than 80 when the incidence of safety events was 6.5% or higher, the power was still considered adequate
when contrasted against the actual upper bound of the 1-sided 97.5% exact binomial confidence interval. Specifically, if 7 of the 100 patients experience a primary safety event, the upper bound of the 1-sided 97.5% exact binomial
confidence interval would be 13.89% and below the 14% threshold. For primary effectiveness endpoint, the power was estimated for an observed
rate between 65% to 80% considering sample sizes from 80 to 100 patients. With a type 1 error rate of 2.5%, 100 patients would have 82.8% power to reject

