13.8.2.2. Primary Safety Endpoint

The primary safety endpoint is 1-year incidence of major stroke in the territory supplied by the treated artery or neurological death. The incidence will be summarized using counts and percentages; the 1-sided

PR-NV16099	Version C	Page 113 of 144		Medtronic
------------	-----------	-----------------	--	-----------

upper bound of the 97.5% confidence limit for the incidence will be evaluated relative to the a priori safety threshold of 14%. Given the primary safety endpoint reported in PMA P100018 was 5.6%, an incidence of ≤7% for the primary safety endpoint would be considered clinically acceptable within the confines of a study of this general size. The hypothesis for evaluating the primary safety endpoint will be evaluated according to the following 2 requirements:

Requirement 1: The incidence of primary safety events must be \leq 7%, and

Requirement 2: The null hypothesis must be rejected in favor of the alternative:

 H_{o} : Incidence at 1-year post-procedure of major stroke and/or neurological death is \geq 14.0%

 H_a : Incidence at 1-year post-procedure of major stroke and/or neurological death is < 14.0%

If the incidence of primary safety events is ≤7% and the upper bound of the 1-sided 97.5% exact binomial confidence interval is <14%, the primary safety endpoint will have been met.

All eligible patients will undergo follow-up at 12 months.

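### Table 13-1 computes safety power as if 8 events in 100 would pass, but the success rule allows only 7, so power is 80.2% falling to 61.4%, not 89.2% falling to 74.7%

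*Combined protocol and SAP*

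**What the plan says.** Section 13.2 bases the safety calculation on 100 patients ("predicated on a population for analysis of 100 patients (with up to 140 subjects enrolled") and on simulations "assuming an observed incidence in the ADVANCE IDE study of primary safety events ranging from 5.6% to 6.9" percent. Table 13-1, titled "Estimated Power Over a Range of Possible Primary Safety Outcomes with 100 Patients (a priori threshold of 14" percent), lists 14 scenarios in steps of 0.1 percentage point. Its column "Actual Type 1 Error Rate" shows 0.0492 in every row, and power runs from 89.19% at 5.6% through 80.96% at 6.4% to 74.72% at 6.9%.

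The text concludes that "Scenarios 1 through 9 reveal a power greater than 80" percent. The sample size part of the synopsis (section 3) says the same: "With 100 patients and an observed incidence of safety event from 5.6% to 6.4%, the power exceeded 80" percent. For rates of 6.5% and above, section 13.2 concedes that power is under 80% but holds that "the power is still adequate when contrasted against the actual upper bound" of the exact interval, because 7 events in 100 give a bound of 13.89%.

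The success rule is in section 13.8.2.2: the endpoint is met "If the incidence of primary safety events is ≤7% and the upper bound of the 1-sided 97.5% exact binomial confidence interval is <14" percent.

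**The concern.** A type 1 error of 0.0492 does not belong to a test built on a one-sided 97.5% bound, whose type 1 error cannot exceed 0.025. Either the table was computed for another test or the rule is misdescribed. The paragraph directly below the table uses the 97.5% bound and takes 7 events as its passing example, so the mismatch lies within one section.

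The defence of the lower power also mixes two things. That 7 of 100 would pass says where the cut-off lies. It does not say how likely a trial is to see 7 or fewer events, and that likelihood is the power.

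At stake is the risk that a device with a safety rate in the sponsor's own planning range misses its primary safety endpoint. Section 13.2 also gives this table as the basis for the 14% threshold, so the figures carry weight beyond description.

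**Working it through.** **Inputs.** n = 100, the 14% threshold and assumed rates of 5.6% to 6.9% (section 13.2, Table 13-1). Success rule: observed incidence at most 7% and one-sided 97.5% exact upper bound below 14% (section 13.8.2.2). X is the number of patients with a primary safety event, binomial with n = 100 and true rate p.

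**Step 1: reproduce the table.** P(X ≤ 8 | 100, 0.14) = 0.0492, the tabulated type 1 error. P(X ≤ 8 | 100, p) gives 89.19% at 5.6%, 80.96% at 6.4% and 74.72% at 6.9%. All 14 entries match to two decimals. The 7-event cut-off does not reproduce the table, nor do normal approximations at one-sided 2.5% or 5% with null or alternative variance. The table therefore counts 8 events as a pass.

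**Step 2: find the cut-off under the plan's rule.** Exact (Clopper-Pearson) upper bounds for n = 100:

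| Events | Observed | 97.5% upper bound | 95% upper bound | Meets the rule |
|---|---|---|---|---|
| 7 | 7.0% | 13.89% | 12.75% | yes |
| 8 | 8.0% | 15.16% | 13.97% | no, fails both parts |

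Eight events clear 14% only with a 95% bound. Each part of the rule by itself limits the count to 7, so no reading of the rule gives 8.

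**Step 3: recompute.** Type 1 error is P(X ≤ 7 | 100, 0.14) = 0.0234. Power is P(X ≤ 7 | 100, p):

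| True rate | Table 13-1 | Under the rule | Difference (points) |
|---|---|---|---|
| 5.6% | 89.19 | 80.22 | 8.97 |
| 5.7% | 88.29 | 78.92 | 9.37 |
| 5.8% | 87.36 | 77.59 | 9.77 |
| 5.9% | 86.38 | 76.23 | 10.15 |
| 6.0% | 85.37 | 74.83 | 10.54 |
| 6.1% | 84.32 | 73.42 | 10.90 |
| 6.2% | 83.23 | 71.98 | 11.25 |
| 6.3% | 82.11 | 70.51 | 11.60 |
| 6.4% | 80.96 | 69.03 | 11.93 |
| 6.5% | 79.77 | 67.53 | 12.24 |
| 6.6% | 78.55 | 66.02 | 12.53 |
| 6.7% | 77.30 | 64.49 | 12.81 |
| 6.8% | 76.02 | 62.96 | 13.06 |
| 6.9% | 74.72 | 61.42 | 13.30 |

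Power reaches 80% only for true rates up to about 5.62%. At a true rate of 7%, P(X ≤ 7) = 59.9%.

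**Step 4: compare with the other primary endpoint.** Section 13.2 gives 82.8% power for effectiveness with 100 patients at 65%, at a type 1 error of 2.5%. That figure reproduces with at least 61 successes (type 1 error 0.0176, power 82.76%). Effectiveness was thus powered at the level the plan states, while safety was powered at about twice its level.

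**The case against.** The strongest reply concerns consequence. The safety rule is stated consistently and is conservative, with an actual type 1 error of 0.0234. The error cannot make the trial pass wrongly and changes no analysis or estimate. Section 13.2 also says that the sample size was first set on precision, about ±5.5 points at an incidence of 8%, so power was not its only basis. And the true rate may be well below 5.6%: section 4.2 reports 2.17% in PREMIER and 3.27% in the ICA population of SHIELD, where the 7-event rule has power of 99.8% and 98.3%. All of this stands and limits the practical urgency. None of it makes the tabulated values right, and the sponsor chose to plan from 5.6%, the rate it cites from PMA P100018. PREMIER also had no large or giant aneurysms, which this trial intends to include.

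Two qualifications on the recomputed figures are fair. They assume exactly 100 evaluable patients, whereas section 13.4 provides multiple imputation for missing endpoint data. But 100 is the table's own premise, and small departures do not help: with 99 patients 7 events fail (bound 14.03%), only 6 pass, and power at 5.6% is 68.1%; with 102 patients 7 events pass and it is 78.8%. Second, the 7% that section 13.8.2.2 treats as clinically acceptable leads into a criterion on the observed rate, so it may not have been meant as a true rate. The 59.9% should be read as the chance of passing if the true rate were 7%.

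**Conclusion.** The point holds as a plain arithmetic error. Table 13-1 is the power of an 8-event, one-sided 5% rule that appears nowhere in the plan. With 100 evaluable patients and complete safety data, power under the actual rule is 80.2% at 5.6% falling to 61.4% at 6.9%, and the claim of more than 80% is true for one of the nine scenarios named. The chance of missing the endpoint is 19.8% instead of 10.8% at a true rate of 5.6%, and 31.0% instead of 19.0% at 6.4%. Type 1 error control and the decision rule are unaffected. A stated power for a primary endpoint, given in two places, should be corrected.

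**What to change.** Recompute Table 13-1 for at most 7 events in 100, with a type 1 error of 0.0234 and the power values in the third column of the table above. Change the conclusions in section 13.2 and in the sample size part of the synopsis to power of 80.2% at 5.6% falling to 61.4% at 6.9%, under the stated condition of 100 evaluable patients. Label the assumed rates as true incidence instead of observed incidence. Delete, in both places, the argument that lower power is adequate because 7 of 100 would pass. Because section 13.2 derives the 14% threshold from this table, the sponsor should confirm that its rationale still stands on the corrected figures.

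The cost is restated text and one table. The correction itself needs no change to the sample size, the thresholds or the conduct of the trial. The stated power becomes less favourable.

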13.3. Analysis Populations

To ensure adequate representation patient with large and giant aneurysms must be enrolled. All primary and secondary endpoints will be analyzed both on an ITT and PP basis. All summarizations and tabulations will be conducted on the ITT population, defined below.

Intent-To-Treat Population: All subjects who were consented and in whom deployment of the Pipeline[™] Vantage Device was attempted (i.e., puncture at the arterial access site), independent of the procedure being completed successfully.

Subject will not be considered part of the ITT population if the puncture at the arterial access site for deployment of Pipeline[™] Vantage Device was not successful. If the puncture at the arterial access site for deployment of Pipeline[™] Vantage Device was successful, the subject will be considered part of the ITT population. Consented subjects who withdraw consent prior to undergoing the study procedure or are found not to meet the inclusion/exclusion criteria prior to undergoing the study procedure, will not be included in the ITT population.

The ITT population will be the primary population for all analyses.

PR-NV16099

The PP population defined below will be used for sensitivity analyses and to provide outcomes for subjects with observed data.

Per-Protocol Population: Per-protocol population is ITT subjects excluding the following subjects:

- Subjects with use of more than 1 treatment device (e.g., coils) other than Pipeline[™] Vantage device during index procedure
- Subjects with failed implantation of study device at index procedure
- Subjects assessed as mRS ≥3 at baseline by independent and certified assessors

